FDA	Food and Drug Administration
GI	Gastrointestinal
hrs	hours
HR	Heart Rate
ID	Identification
min	minutes
mm	millimeters
NPV	Negative Predictive Value
PPV	Positive Predictive Value
psi	Pounds per Square Inch pressure unit
PT/INR	Prothrombin Time/International Normalized Ratio
SADE	Serious Adverse Device Effect
SAE	Serious Adverse Event
SOP	Standard Operating Procedures
TASMC	Tel Aviv Sourasky Medical Center
UADE	Unanticipated Adverse Device Effect
USADE	Unanticipated Serious Adverse Device Effect

Date issued:
05 Dec2018

SUBJECT: Functionality and Accuracy of the smART System in Real-Life ICU Settings

Number: CLT3_SY_P001

Revision 08

Page 5 of 38

Synopsis

Study Title:	Functionality and Accuracy of the smART System in Real-Life ICU Settings
Purpose:	To validate the functionality and accuracy of the smART System in areal-life ICU setting
Study Design:	Open, prospective, single arm study
Study Objectives:	
1. To verify that the system is able to automatically detect correct placement and tube movement during on-going use2. To record and analyze impedance levels and reflux episodes3. To verify that the system stops feeding when the tube is misplaced or reflux is detected4. To obtain feedback from clinical staff regarding device use and usability5. To Collect data regarding the occurrence of reflux episodes in relation to patient positioning6. To quantify the amount of discarded nutritional supplement7. To demonstrate the safety of the smART system8. To evaluate the effectiveness of the System to reduce aspiration of gastric contents.
No. of Subjects:	20 subjects
Population:	
- ICU ventilated patients- Patients who are receiving PPI therapy during the study- Patients receiving a standard enteral feeding formula- Patients who are hemodynamically and respiratory stable
Investigational Sites:	Thomas Jefferson University
Principal Investigator:	[name], MD
Study Duration:	56 hrs. -7 days per patient.

smART Healthcare
PATIENT SAFETY THROUGH TECHNOLOGY

Date issued:
05 Dec2018

SUBJECT: Functionality and Accuracy of the smART System in Real-Life ICU Settings

Number: CLT3_SY_P001

Revision 08

Page 6 of 38

Endpoints:	Overall duration of study is estimated to be 3 months (depending on enrollment rate).
	
Primary:
 
Functionality
 
- the system is able to accurately guide the user to ensure correct initial placement (verified by X-ray).- the system is able to detect tube movement/displacement during ongoing use (verified by markings on the tube).- the system automatically stops feeding when tube displacement is detected.- the system automatically stops feeding when reflux is detected.- the system automatically inflates the balloon when a reflux episode is detected 
Safety
 
- occurrence of device related adverse events 
Secondary:
 
- Ease of use of the system and the user interface by subjective questionnaire of staff.- Recording of impedance detected by the system and correlation to patient positioning.- Quantification of the amount of discarded nutritional supplement by implementing GRV test as needed and according to hospital procedures.- Reduction of aspiration of gastric contents percentage compared to standard feeding (as reported in literature).- Correlation between patient clinical information and the occurrence of reflux and sensors data.
Inclusion Criteria:	
1. Males and females 18 years or older2. Patient has already been admitted to ICU3. Patient requires enteral feeding4. Patients receiving PPI therapy

PATIENT SAFETY THROUGH TECHNOLOGY

Date issued:
05 Dec2018

[figure not shown]
SUBJECT: Functionality and Accuracy of the smART System in Real-Life ICU Settings

Number: CLT3_SY_P001

Revision 08

Page 7 of 38

	
5. Informed consent by independent physician and next of kin6. ICU ventilated patients
--	---

1 Identification and Description of the Investigational Device

1.1 Introduction

Supplemental enteral nutrition is commonly used for various indications such as swallowing disorders, inability to ingest food (e.g. head injury, stroke, and anorexia due to an underlying disease) and others. The majority of patients requiring nutritional support will need it for less than one month, and nasogastric tube feeding is by far the most commonly used route of access.

There are a number of potential complications that can occur with naso-enteral tube feeding, the most noted complications are:

Preventing aspiration of gastric content in tube-fed patients

The central cause of **aspiration pneumonia in tube-fed patients is due to aspiration of gastric contents**. There are various tube-fed nursing practices that may help reduce the rate of aspiration, but their efficacy is limited and they are hard to implement. Currently there are no device-based solutions for prevention or monitoring of gastric content aspiration. Aspiration pneumonia (including pneumonitis) has been reported to occur in average of 25-30% of tube fed patients in ICU and ICU 44% to 95% in neuro ICU. In critically ill ventilated patients, enteral nutrition has been shown to be an independent risk factor, increasing the risk for the development of pneumonia by more than five-fold (Drakulovic, et al. 1999). Many researchers believe that in tube-fed critically ill patients it is aspiration of gastric contents that is of greatest concern (Metheny, et al. 2006).

Usually, gastric residual volume tests are routinely performed every 4 hours. These tests **take up valuable nursing resources, are inaccurate, and often lead to unnecessary cessation of feeding**. Gastric emptying of calorie-dense liquid meal is 40%-45% slower in mechanically ventilated patients (Ritz, et al. 2001). Delayed gastric emptying is even more frequent in patients with burns, multiple trauma (with and without head injury) and severe sepsis.

The term “gastrointestinal failure” (GIF) has been used to describe a syndrome of severe gastroparesis. This syndrome is more commonly observed in patients with acute medical and surgical emergencies than in patients undergoing elective surgery and typically develops several days after admission to an ICU. A retrospective study found a 10% incidence of gastrointestinal failure in ICU patients (Mizock 2007).

There exists an urgent need for device and method for the prevention of aspiration pneumonia.

Positioning nasogastric feeding tubes

Insertion of nasal feeding tubes can be performed blindly at bedside or with fluoroscopic or endoscopic guidance into the stomach.

SUBJECT: Functionality and Accuracy of the smART System in Real-Life ICU Settings

Number: CLT3_SY_P001

Revision 08

Page 9 of 38

[figure not shown]
Although generally safe and effective, they are usually inserted blindly at the bedside and there is a wide spectrum of known complications associated with feeding tube placement. The most common serious complication is misplacement of the feeding tube into the bronchial tree with resulting pneumonitis, pneumonia, and/or pneumothorax if not recognized. This is reported to occur in **2.4%–3.2% of nasogastric insertions** (James L, et al. 2012).

Recent studies have suggested that 0.1 to 0.3% of all patients who were blindly placed of their feeding tubes die as a result of bronchopulmonary injury from misplaced tubes (Sorokin R et al. 2006) (Aguilar-Nascimento JE, et al. 2007).

It is estimated that approximately **1.2 million feeding tubes are placed each year in the United States alone** (Koopmann MC et al. 2011). If these tubes were placed blindly this would translate to **3,600 to 8,400 pulmonary injuries, and 1,200 to 3,600 deaths in the United States each year**. Hundreds of thousands of patients require NG tubes each year in the UK. Although the precise number is not known, the NHS Purchasing and Supply Agency (PASA) which distributes NG tubes has estimated that between 750,000 to 1,000,000 tubes are used each year within the NHS1. In addition to those used within the NHS, private hospitals, hospices and nursing homes are expected to greatly increase the number of tubes used annually. Currently, X-ray is the gold standard method for detecting the position of nasogastric tubes (Hedberg et al, 2005). However, staff does not use it routinely due to cost, risk of radiation exposure, and delay in feeding (National Patient Safety Agency, 2011; 2005). In addition, the National Patient Safety Agency (NPSA) has drawn attention in 2011 to the risk of misinterpretation of X-rays used to confirm the position of a nasogastric tube. Positioning complications are also occurring throughout the duration of the use of the tube. Movement of the distal tip of the feeding tube occurs even when the NG tube is taped in place. This is most likely to occur with soft, small-bore NG tubes. Malpositioning of the indwelling tube may result in injury or aspiration.

The smART™ Feeding Tube System is a novel feeding tube developed by ART Healthcare Ltd. to overcome feeding tube displacement and reflux prevention and the complications associated with them. The smART Feeding Tube is equipped with sensors designed to provide information about the location of the tube tip relative to the lower esophageal sphincter as well as a balloon intended to aid in the prevention of aspiration due to reflux episodes.

The aim of the clinical study proposed in this protocol is to assess this new device in the clinical setting model.

1.2 Device Description

[figure not shown]
The smART™ Feeding Tube System (sFTS) is a novel system with feeding tube developed by ART Healthcare Ltd, based on sensor-lined tubes that transmit real-time information to an external console. The smART™ feeding tube is equipped with a balloon which serves as an anti-reflux mechanism to prevent the gastric contents from regurgitating to the upper portion of the esophagus thus reducing the risk for aspiration. In addition, the smART™ feeding tube is equipped with sensors designed to provide information about the location of the tube tip relative to the lower esophageal sphincter (LES) thus assisting in reducing the incident of misplacement during first positioning. The smART™ feeding tube is also connected to a motorized mechanism which automatically and in real-time stops feeding if the feeding tube moves out of position during ongoing use or detect gastric content in esophagus. Furthermore, smART™ Feeding Tube System can guide operator to correctly re-position the tube in case of tube migration while feeding.

To minimize the risk of pressure build-up in the stomach and esophagus as a result of the balloon inflation, the company has added an additional safety feature (figure 2). This feature allows for gastric content to escape through the feeding tube into a collection bag. The concept behind this mechanism is simple, once the console detects a reflux episode it automatically stops feeding via clamping and inflates the balloon. The safety feature triggers a release clamp to open, thus allowing gastric content to climb up the feeding tube and release any pressure that may raise within the patients' stomach upper GI tract.

The smART™ Feeding Tube System contains the following (figures 1, 2 and 3):

a) **Feeding tube** – consisting of the following:

- Multi-lumen, made of medical grade material (figure 1a)
- Y-Shaped Feeding inlet, with standard dimensions, made of medical grade material and compatible with ENfit connectors for feeding set and GJV Drainage bag connections, as shown in figure 1b. The Y – Shaped port also connects to a gastric content bag. This feature was added to overcome risks associated with pressure build-up in the stomach and esophagus due to balloon inflation. Gastric contents will pass through the feeding tube and accumulate in the connected collection a bag (figure 2).
- Impedance sensors, which are made of medical grade SS316 wire. The sensors are located in a number of locations along the feeding tube as well as above the balloon to allow the

system to identify whether it actually prevented the gastric content from climbing up the esophagus.

- Hybrid connector, which has PCB electric contacts and one air conduit – Not in contact with the feeding liquid or the patient body.
- Balloon made of medical grade material.

[figure not shown]

Figure 1: a) smART™ Feeding Tube and feeding connector. b) ENfit connectors for feeding set and GRV Drainage bag connections

1. Y connector- ENFit connection to feeding set
2. Y connector- ENFit connection to GRV Drainage bag
3. smART™ Feeding Tube hybrid connector- feeding tube connection to HUB inlet.
4. smART™ Feeding Tube with Sensors
5. Balloon

b) **Electronic console (12V power supply operated) which:**

- Indicates the location of the tube in the body.
- Inflates and deflates the balloon as needed
- Stops the feeding when feeding tube is out of position during ongoing use.
- Keeps a patient event log The electronic console components include:
- Electronic box, which serves as the interface for the system.

- Stand AC adapter, which allows connecting the electronic console to standard IV stand pole.

c) The Hub:

- The smART™ HUB (Figures 2 and 3) is located at the bedside mounted on a pole. It is connected to the rear panel of the console using a “build in” cable that comes out from the Hub.
- ~~Additional connection between smART™ ENFit feeding inlet of the feeding tube Y connector.~~
- The smART™ Hub has an indicator light that shows the HUB's state

Figure 2: the smART Feeding Tube System

[figure not shown]
[figure not shown]

Figure 3: Pressure Build-Up Safety Mechanism

1.3 Intended Use

The smART™ Feeding Tube is intended for gastric decompression, gastric lavage, and the administration of nutrition, fluids and medications for patients who have an intact gastrointestinal tract but are physically unable to manage nutritional intake through normal mastication and deglutition

The smART™ Feeding Tube System serves as an anti-reflux mechanism, by using a balloon, which prevents the gastric contents from regurgitating to the esophagus thus reducing the risk for aspiration of patients requiring enteral feeding. The smART™ System is also designed to aid qualified operators in the placement of the smART™ Feeding Tube into the stomach during initial placement thus assisting in reducing the incidence of misplacement during first positioning. Furthermore, smART™ Feeding Tube monitors the position continuously during the course of the feeding and automatically provides real time alerts of tube migration. smART™ System also can guide the operator to correctly reposition the tube.

1.4 Intended Users and Training Requirements

The smART™ System is indicated for the same patient population as other commercially available feeding tubes, namely, patients in need of enteral feeding and administration of medications. The smART™ feeding tube will be introduced to patients by the medical staff qualified to introduce commercially available feeding tubes. During site initiation, all site staff that have been identified as device operators will receive training by the sponsor in order to ensure correct use of the device throughout the study.

1.5 Manufacturer and Manufacturing Information

The smART™ System was designed and is manufactured by Art Healthcare. Details on the manufacturing of the system are provided in the Investigator's Brochure.

1.6 Device Procedure

The use of the smART™ System is substantially similar to the use of commercially available feeding tubes. The smART™ System includes the added feature of facilitating correct tube placement and alerting when tube is displaced during ongoing use. The system will automatically stop feeding if displacement is detected. If a reflux episode is detected by the system, a balloon located on the tube will automatically inflate to prevent gastric content from regurgitating to the esophagus. The balloon inflation parameters are as follows:

[figure not shown]
- Maximum balloon pressure: 30 mmHg
- Maximum inflation duration: 5 minutes
- Minimum duration between balloon inflations: as long as the previous inflation period

2 Risks and Benefits

The smART™ System is designed according to international standards for medical devices. Compliance with these standards ensures that the device can be used safely in humans.

Biocompatible materials are used for the feeding tube components. The use of biocompatible materials should protect the patient against possible biomaterial related adverse events.

ART Healthcare follows and complies with the risk management standard ISO 14971:2012 and ISO 14971:2007. Extensive design verification & validation bench and animal tests were performed to mitigate all risks detected, in accordance with essential requirements listed in the Medical Device Directive (MDD 93/42/EEC).

SUBJECT: Functionality and Accuracy of the smART System in Real-Life ICU Settings

Number: CLT3_SY_P001

Revision 08

Page 15 of 38

In addition, a feasibility study on 10 healthy volunteers was completed with the (smART™ System).

The results of the study supported the company's claim that the insertion, balloon inflation and feeding with the smART™ feeding tube are safe and tolerable. The results also show that the device aids in the correct placement of the feeding tube into the patient.

2.1 Anticipated Clinical Benefits

The purpose of this study is to evaluate the ability of the system to aid in the correct initial placement of the feeding tube, detect tube malpositioning during ongoing use, as well as prevent gastric content from regurgitating to the esophagus. With validation of the above features during the study, the clinical benefit of the device will be the lowering of risks associated with tube displacement and malpositioning as well as lowering the risk associated with reflux and aspiration.

2.2 Anticipated Adverse Device Effects

Mild discomfort in the throat is anticipated with the insertion of the feeding tube, as with all other feeding tubes which are used in clinical situations. Minor internal skin irritation may occur due to balloon inflation.

2.3 Residual Risks Associated with the Investigational Device

No residual risk is anticipated with the investigational device.

3 Study Objectives

The primary objectives of this study are:

1. To verify that the system is able to automatically detect correct placement and tube movement during on-going use
2. To record and analyze impedance levels and reflux episodes
3. To verify that the system stops feeding when the tube is misplaced or reflux is detected
4. To obtain feedback from clinical staff regarding device use and usability
5. To Collect data regarding the occurrence of reflux episodes in relation to patient positioning
6. To quantify the amount of discarded nutritional supplement
7. To evaluate the effectiveness of the system to reduce aspiration of gastric contents.

PATIENT SAFETY THROUGH TECHNOLOGY

Date issued:
05 Dec2018

SUBJECT: Functionality and Accuracy of the smART System in Real-Life ICU Settings

Number: CLT3_SY_P001

Revision 08

Page 16 of 38

4 Study Endpoints

4.1 Primary Endpoints

Functionality

- the system is able to accurately guide the user to ensure correct initial placement (verified by X-ray)
- the system is able to detect tube movement/displacement during ongoing use (verified by markings on the tube)
- the system automatically stops feeding when tube displacement is detected
- the system automatically stops feeding when reflux is detected
- the system automatically inflates the balloon when a reflux episode is detected

Safety

- occurrence of device related adverse events

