6.2.2 Treatment

Following the screening procedure staff will utilize the smART System to provide enteral feeding to the patient. Feeding tube insertion and commencement of feeding should be done per patients' need and per local hospital procedures.

6.2.3 Study Specific Procedures:

- Videotaping of subject

Following the completion of the informed consent procedure and prior to feeding tube placement, a video recording of the patient will commence. The camera will be placed across from the patient focusing on the facial area and will allow recording of any movement of the tube for later comparison with the data logs recorded by the smART console. All recorded data must be attached to the CRF and serves as an integral part of the analyzable data for the study.

Specific video procedures will be supplied to the site as part of the study MOP binder.

- Initial Tube Placement:

Vital signs should be noted within 10 minutes of feeding tube insertion.

Study staff should follow the device instructions for use and specific instructions provided by the console during initial tube placement. Time of tube placement is recorded by the console.

Once initial placement is confirmed by the system, verification of correct placement should be performed by abdominal X-ray (gold standard). Note: X-ray should be performed as needed and according to hospital procedures. Once placement confirmation is obtained via x-ray, staff should use a permanent marker to indicate the edge of the nostril on the feeding tube (this mark will enable the staff to verify malpositioning warnings if they occur during on-going use).

- **Ongoing Use**

If system alerts of tube displacement during ongoing use, staff should record the event and verify based on the tube marking if malpositioning occurred and document the event. The need for tube reinsertion/repositioning should be evaluated and performed as needed.

When a reflux episode is detected by the system, the following will be initiated:

1. feeding stops
2. feeding tube balloon will automatically be inflated by the system
3. an alert will sound
4. The Y-piece block opens allowing for feeding system decompression initiating free flow of gastric content into the collection bag. The system will automatically record data relevant to reflux episodes and store it.

- **Feeding Information**

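### The primary endpoint is tube movement or displacement, but the bedside check that verifies it asks about malpositioning with no distance set, so an alert on a small real shift can be read either way

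*Combined protocol and SAP*

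**What the plan says.** The second functionality endpoint in section 4.1 (repeated in the synopsis) is that "the system is able to detect tube movement/displacement during ongoing use (verified by markings on the tube". The next one is that "the system automatically stops feeding when tube displacement is detected".

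The verification is described in section 6.2.3. After X-ray confirmation, staff mark the tube at the edge of the nostril. Under Ongoing Use, if the console gives a displacement alert, "staff should record the event and verify based on the tube marking if malpositioning occurred and document the event". No distance, direction or tip position is given for that judgement.

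Other places use other words. In section 3, objective 1 is "To verify that the system is able to automatically detect correct placement and tube movement during on-going use" and objective 3 is "To verify that the system stops feeding when the tube is misplaced or reflux is detected". Under Videotaping in section 6.2.3, the camera "will allow recording of any movement of the tube for later comparison with the data logs recorded by the smART console", and the recorded material "serves as an integral part of the analyzable data for the study".

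**The concern.** The endpoint and the bedside check share one reference, the nostril mark, but ask different questions of it. A slide of the mark is movement. Whether it amounts to malpositioning depends on a threshold, and the protocol gives none. The judgement is left to staff who have just heard the alert.

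The share of alerts confirmed by the mark is thus open to two readings on a primary endpoint, and the choice could be made after the data are seen. It also bears on the stop-feeding endpoint, which is conditional on displacement having been detected. If the shift is not measured at the time, it may be lost once the tube is repositioned.

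**Working it through.** **Planning figure.** There is nothing to reproduce. Section 9.1 gives 20 subjects and descriptive statistics, with no target rate, expected number of alerts, alpha or power. Section 9.2 does not define a true detection, a false alert or a miss.

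**Wording side by side.**

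| Place | Event term | Reference named | Distance |
|---|---|---|---|
| 4.1, second functionality endpoint | movement or displacement | tube mark | none |
| 4.1, third functionality endpoint | displacement | none | none |
| 3, objective 1 | movement | none | none |
| 3, objective 3 | misplaced | none | none |
| 2.1 | malpositioning | none | none |
| 6.2.3, Ongoing Use | displacement alert, checked for malpositioning | tube mark | none |
| 6.2.3, Videotaping | any movement | video against console log | none |
| 1.2 | out of position, migration (sensors locate the tip relative to the sphincter) | none | none |

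**Tracing each situation through 4.1 and the bedside check.**

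1. Alert, mark has not moved: unconfirmed under both.
2. Alert, large shift of the mark: confirmed under both.
3. Alert, small real shift: a detection under 4.1. At the bedside it depends on whether staff call it malpositioning.
4. No alert: the bedside check is not triggered, so it yields no result.

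Only situation 3 gives two answers.

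**Illustration (all inputs assumed).** Let f be the share of real shifts that staff would call malpositioned, and g the share of the remaining small shifts on which the console alerts. Assume that it alerts on every malpositioned tube and that every alert follows a real shift. Under the movement wording, the confirmed share of alerts is 100% by construction. Under the malpositioning wording it is

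f / (f + g(1 − f)).

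| f | g = 0 | g = 0.5 | g = 1 |
|---|---|---|---|
| 0.25 | 100% | 0.25/0.625 = 40% | 25% |
| 0.50 | 100% | 0.50/0.75 = 67% | 50% |
| 0.75 | 100% | 0.75/0.875 = 86% | 75% |

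For scale, assume one alert in each of 20 subjects, with f = 0.75 and g = 1. The same alerts read as 20/20 (exact Clopper-Pearson 95% interval 83.2% to 100%) or 15/20 (50.9% to 91.3%).

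**The case against.** The strongest reply is that this is loose vocabulary. In section 6.2.3 the text runs from a displacement alert straight to a check for malpositioning, and it describes the mark as a means of verifying malpositioning warnings, evidently the same alerts. Section 2.1 states the purpose in terms of malpositioning. The endpoint and the check use the same mark. The study is descriptive, with no pass mark, so nothing formally succeeds or fails.

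Much of that stands, and it rules out three stronger readings that a reader might infer:

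- *That the protocol holds three rival definitions of the event.* None of these passages is a definition. The words are used interchangeably, and what is missing is a criterion.
- *That a silent small shift counts as a miss in one place and as correct silence in another.* The bedside check follows an alert only, so it never assesses a silent shift. The video sentence says what is recorded. It does not say that each movement without an alert is a missed event, and the detailed video procedures are in a manual outside these documents.
- *That staff record only a yes or no, so that the data can never be re-scored.* The CRF is not in the documents and may hold more, and video and console logs are kept.

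The reply does not supply a distance. Even if the terms are synonyms, staff must still decide how far the mark has to move before they confirm the alert, and two nurses could document the same shift differently.

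**Conclusion.** The point holds as a gap in the verification of one primary endpoint. The endpoint wording accepts movement. The check that verifies it asks about malpositioning without a criterion, and the protocol text does not ask for the measured shift. The consequence is limited to alerts on small real shifts.

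Its size is unknown. In the illustration the gap runs from nothing, if the console never alerts on small shifts, to 75 percentage points (100% against 25%) at the far corner of the assumed range. These figures say nothing specific about this device. The scoring consequence is inferred from the wording, since the plan has no rule for classifying an alert.

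This is a change the sponsor should make because it is cheap and because a shift not measured at the alert may not be recoverable. It does not invalidate the study.

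**What to change.** 1. At each displacement alert, have staff record the measured mark-to-nostril shift in cm and its direction before any repositioning, in place of the unthresholded malpositioning judgement. This adds a measurement only. Whether to reposition is decided as section 6.2.3 already provides.
2. Use one event term in the synopsis, sections 3 and 4.1, and both parts of section 6.2.3. Attach a distance criterion that the sponsor fixes before the first patient and justifies independently of the observed alerts.
3. Name the tube mark as the deciding reference, as section 4.1 implies, with the video as supporting evidence.
4. In section 9.2, plan to report all alerts by measured shift, including those with no shift or a shift below the criterion. Alerts below the criterion stay in the false-alert count.

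The cost is protocol wording, one CRF field and a few seconds per alert. The downside for the sponsor is that some alerts may no longer count as confirmed. One limit remains: the mark shows movement at the nostril, while section 1.2 says the sensors locate the tip, so the criterion is a proxy and its justification should say so.

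### The two feeding-stop endpoints and the balloon-inflation endpoint name no independent check, so a stop failure that the console does not register could go unseen.

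*Combined protocol and SAP*

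**What the plan says.** Section 4.1 lists five functionality endpoints. Two carry their own reference:

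- Initial placement is judged against an image: "the system is able to accurately guide the user to ensure correct initial placement (verified by X-ray".
- Later movement is judged against the nostril mark: "the system is able to detect tube movement/displacement during ongoing use (verified by markings on the tube".

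Three carry none:

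- Feeding stop after displacement is worded thus: "the system automatically stops feeding when tube displacement is detected".
- Feeding stop after reflux has a parallel wording: "the system automatically stops feeding when reflux is detected".
- Balloon inflation comes last in the list: "the system automatically inflates the balloon when a reflux episode is detected".

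Section 6.2.3 (Ongoing Use) says what happens at an alert. For displacement, "staff should record the event and verify based on the tube marking if malpositioning occurred", and they document it. For reflux, the section lists four automatic responses: feeding stops, the balloon inflates, an alert sounds and the Y-piece opens to the collection bag. It then says: "The system will automatically record data relevant to reflux episodes and store it". It asks for no staff observation at a reflux alert.

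The study video, also in section 6.2.3, is meant to capture tube movement for comparison with the console logs: "The camera will be placed across from the patient focusing on the facial area".

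Section 1.2 gives the console three relevant jobs: stopping feeding, driving the balloon and keeping the patient event log. Sections 9.1 and 9.2 plan descriptive statistics in 20 subjects. They give no data source, event definition or success criterion for these three endpoints.

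**The concern.** Primary objective 3 in section 3 is to verify that feeding stops when the tube is misplaced or reflux is detected. Verification needs something other than the device to show that flow stopped. The protocol supplies this for initial placement and for tube movement, but not for the actions the device takes after detection.

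If a clamp leaked or jammed and the console did not register it, no planned observation at the alert would show the failure, and the event could be counted as a success. This cannot be repaired at analysis, because whether feed was flowing at the time of an alert cannot be recovered later if nobody recorded it.

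**Working it through.** **Step 1. Look for an outside, event-level check in each data source.** No figure in the plan is in dispute, so this step is a reading.

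| Source (section) | Independent of the device? | Shows whether flow stopped or the balloon inflated at a given alert? |
|---|---|---|
| Staff check at a displacement alert (6.2.3) | Yes | No. It tests tube position against the nostril mark |
| Reflux data stored by the system (6.2.3) | No | Contents not described |
| Console event log (1.2) | No | Contents not described |
| Impedance sensors above the balloon (1.2) | No | Concern whether gastric content passed the balloon; part of the same device |
| Video (6.2.3) | Yes | Framed on the face, for tube movement |
| Feeding times and amounts, gastric residual volume (6.2.3) | Yes | Taken from hospital records at the end of each patient's study; not linked to alerts |
| Tracheal samples for pepsin (6.2.3, 6.2.11) | Yes | No. They measure aspiration, one sample every 8 hours |
| Endoscopy in a subset (6.2.3) | Yes | No. It looks for trauma |
| Usability questionnaire (Appendix 2) | Yes | No item asks whether feeding stopped |

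On the tracheal samples: section 1.6 caps an inflation at 5 minutes, and the sampling interval is 8 × 60 = 480 minutes. One inflation therefore covers at most 5/480 = 1.0% of an interval, so a sample cannot confirm an individual inflation.

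No source is both independent and informative about flow or inflation at the level of the alert.

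**Step 2. Would more events help?** This is an illustration on assumed values. The documents give no failure rate and no expected number of alerts. Let f be the true failure rate per actuation, u the share of failures that the console does not register, and n the number of independent events. If only device-recorded data are used:

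P(at least one failure seen) = 1 − (1 − f(1 − u))^n

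With n = 20:

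| f | u = 0 (every failure visible) | u = 0.5 | u = 1 (none visible) |
|---|---|---|---|
| 5% | 64% | 40% | 0% |
| 10% | 88% | 64% | 0% |
| 20% | 99% | 88% | 0% |

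The u = 1 column stays at 0% for any n.

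**Step 3. What would a clean device record bound?** With no failures in n events, the exact two-sided 95% upper limit is 1 − 0.025^(1/n): 16.8% for 0/20, 7.1% for 0/50 and 3.6% for 0/100. These limits apply only to failures that the record can register. They put no bound on the others.

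Steps 2 and 3 show the structure of the problem. They do not estimate its size in this trial, because u is unknown.

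**The case against.** A reader might infer that the three endpoints rest solely on the device log, and that they merely compare the console's command with the console's own entry. The documents do not support that. Section 4.1 names no source for these endpoints and neither does section 9.2. Nothing says whether the log holds commands or sensed states such as balloon pressure. The study manual binder, the user manual and the case report forms are not in the documents, so what staff record per event cannot be fully known.

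Some outside data could also reveal a gross or lasting failure by chance: charted feeding amounts, the collection bag, or staff notes at a displacement alert. This is a descriptive study of 20 subjects with no success threshold for a bias to cross. It follows bench and animal testing and a feasibility study in 10 healthy volunteers (section 2).

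These arguments limit the claim to a missing reference and keep its importance modest. They do not supply the reference. None of the outside data is tied to these endpoints or captured alert by alert, and nothing in the protocol tells staff to look at the flow.

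**Conclusion.** The point holds as a gap in verification. Three of the five primary functionality endpoints have no specified independent check, while the other two do. For reflux, the only event-level source the protocol names is data from the device under test. For displacement, the staff check does not address flow. A stop failure that the console does not register could go unseen.

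The size cannot be derived from the documents. Assuming a silent-failure rate and quoting it as the error would only return the assumption. The stronger conclusion, that the endpoints are known to be biased upward, does not follow either. It would require knowing what the log records and whether such failures occur.

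This is a worthwhile improvement, not a fatal flaw. The conclusion rests on the protocol as written and could soften if the case report forms or study manual already call for a flow check.

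**What to change.** In section 6.2.3, add a short timed record for each alert that staff attend. For displacement it extends the documentation already required; for reflux it is new. Items:

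- time of the observation;
- feed flow seen stopped (yes/no);
- for reflux only, line to the collection bag open (yes/no).

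In section 9.2:

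- Report each of the two stop endpoints as staff-confirmed stops divided by attended alerts.
- Show log-only alerts separately, with their number.
- State that attended alerts may be a selected subset, since short events can clear before anyone arrives.
- Report balloon inflation as device-reported and not independently verified. The bedside record does not reach it, and copying a console reading of balloon state would still be device data.

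Cost: a brief added record at reflux alerts and slightly more documentation at displacement alerts. The remaining limitation is that alerts cleared before staff arrive stay log-only, which the separate count makes visible.
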